6.4 Sample Size and Power

A power analysis is not applicable for this pilot study due to the small number of subjects intended to be recruited solely for the purpose of determining the feasibility of conducting described study procedures.

6.5 Interim Analysis

The study will be stopped for any individual participant if the reported level of discomfort described by the participant in their journal entries or meditation logs is considered to be more than minimal by a trained clinical psychologist (Co-PI), if their DASS-21 scores increase significantly from one visit to the next, or if they report that the study procedures themselves have contributed to any discomfort/distress.

STUDY INTERVENTION

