Study Duration	
 • Each subject will undergo 4 weeks of intervention or control group training, a pre- and post-training visit, and a 1-month follow-up. • The entire study is expected to last 3 months.
Study Phases	(1) Subjects screened for eligibility and obtaining consent;
Screening	(2) Cognitive task performance, blood sample collection, surveys;
Study Treatment	(3) Four weeks of virtual training in Koru mindfulness or an age- and time-matched comparison group;
Follow-Up	(4) One-month follow up online surveys
Efficacy Evaluations	
 • Mean number of visits attended by participants and total number of journal entries.
Pharmacokinetic Evaluations	N/A
Safety Evaluations	Self-report measures of anxiety, depression, and stress will be evaluated at the beginning of each visit to determine any changes that could be in result of the intervention.
Statistical And Analytic Plan	
 • To assess the primary objective (feasibility) of the study, the primary outcome will be the count of participants in each of the 6 visits, and the number of surveys that are completed at the 1-month follow-up contact. • To assess the secondary objective (participant compliance), the secondary outcome will be measured by total journal entries submitted during the 4 weeks of intervention training.
DATA AND SAFETY MONITORING PLAN	The Co-Investigators will review participants' experiences with study procedures on a weekly basis. Meditation practice may elicit discomfort if traumatic memories resurface or the participant is experiencing high stress. The Koru teacher is trained in trauma-sensitive mindfulness and has implemented this awareness in the design of the visits. Nonetheless, the teacher will regularly check in with students to address any concerns.

BACKGROUND AND RATIONALE

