4.3 Follow- up procedures (by visits)

One month after the conclusion of visit 6, participants will be recontacted via email with a link to REDCap to complete several surveys.

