4.4 Subject Completion/ Withdrawal procedures

Participants will be screened for drug and alcohol use upon arrival to visits 1 and 6. If the test results from a urine sample and breathalyzer are positive, subjects will be withdrawn from the study. If participants in the KM group are experiencing extreme discomfort during weeks when visits 2-6 take place, due to resurfacing of traumatic experiences, subjects will be withdrawn from the study and given resources (see attachments) to alleviate distress. Investigators may also terminate an individual's participation if the subject is uncooperative or otherwise behaves in a way that makes study personnel feel uncomfortable or unsafe.

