5.4 Safety Evaluations

The DASS-21 will be used to measure depression, anxiety and stress and will be administered at the beginning of each visit. Scores will be used to evaluate any within-subject changes that may prompt further review. The KM instructor will read logs daily and determine if any participant should be followed up with.

STATISTICAL CONSIDERATIONS

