6.2 Secondary Endpoint

1. Participant satisfaction [Time Frame: 4 weeks]
 - a. Feedback will be collected the same day as each training visit, using a simple survey designed on Qualtrics.
2. Depression, Anxiety, and Stress Scale (DASS-21) [Time Frame: 8 weeks]
 - a. The DASS-21 consists of three self-report scales used to measure depression, anxiety and stress. This is a shortened form of the original DASS [36], which contains 42-items but shows no improvement over the 3-factor model for the 21-item scale [41]. The DASS-21 has been validated in non-clinical samples, and may even be used to measure an overall level of psychological distress [42]. In a non-clinical sample of Greek adults 18 years of age and older, the DASS-21 showed satisfactory reliability, with Cronbach alphas of 0.85, 0.84, and 0.84 for the depression, anxiety and stress scales, respectively [43]. There was also high convergent and discriminant validity of the three scales in this same sample.
3. Credibility/Expectancy Questionnaire (CEQ) [Time Frame: 1 week]
 - a. Questions on the CEQ are used to measure the credibility of an intervention and treatment expectancy in clinical studies [27]. However, due to methodological limitations of comparison groups for mindfulness meditation (e.g., waitlist control group doesn't match intervention in any

way), evaluating the credibility of the control group intervention and the expectation of benefit to participants in both groups will facilitate the design of better comparison groups than those that currently exist.

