6.3 Statistical Methods

The total number of eligible participants will be used as a measure of successful recruitment strategies and feasibility of enrollment criteria. The mean number of self-report training or journaling days recorded by participants and the total number of visits attended by each participant will be used as measures of compliance with study procedures. The number of times discomfort is reported by participants with any training procedure will be used as a measure of safety. A within-subjects ANOVA will be used to analyze the change in DASS-21 scores across the training visit weeks, including the total score and scores for all 3 subscales. A 1-Sided t-Test will be used to analyze the mean difference in CEQ score between the intervention and control group.

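### Section 6.5 stops participants on a DASS-21 rise and nothing provides for DASS-21 afterwards, so a complete-series ANOVA would usually, though not always, understate worsening

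*Combined protocol and SAP*

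**What the plan says.** - **Stopping rule (6.5).** "The study will be stopped for any individual participant" on any of three grounds. One is "if their DASS-21 scores increase significantly from one visit to the next". No threshold is given, and neither the total score nor a subscale is named.
- **Endpoint status (6.2, synopsis).** The secondary endpoints include "Depression, Anxiety, and Stress Scale (DASS-21) [Time Frame: 8 weeks". The synopsis makes the same self-reports the safety evaluation: they "will be evaluated at the beginning of each visit to determine any changes that could be in result of the intervention".
- **Schedule (5.4).** "The DASS-21 will be used to measure depression, anxiety and stress and will be administered at the beginning of each visit". The visit 2 score is therefore taken before the first class, and a rise from visit 1 to visit 2 can trigger a stop. Section 5.4 adds, more mildly than 6.5, that changes within a participant may lead to more review.
- **Analysis (6.3).** "A within-subjects ANOVA will be used to analyze the change in DASS-21 scores across the training visit weeks", for the total and all three subscales. There is no rule for incomplete series.
- **After a stop (4.3, 4.4).** The only later contact is timed from visit 6: "One month after the conclusion of visit 6, participants will be recontacted via email". Section 4.4 says of KM participants in extreme discomfort that "subjects will be withdrawn from the study and given resources (see attachments) to alleviate distress", and describes no later assessment.

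**The concern.** The score that decides who is stopped is the score being analysed. A conventional repeated-measures ANOVA needs every visit from every participant. If a stop ends collection, the people whose scores rose most sharply are the ones dropped, and those who remain look better than the group as randomised. There would also be no planned DASS-21 record of whether a stopped participant's distress resolved.

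What is at stake is a secondary and safety endpoint. Stops lower the retention counts, but those counts record them correctly, so the primary feasibility assessment is not biased.

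**Working it through.** **No plan figure to reproduce.** The documents give no DASS-21 SD, reliability, effect size or trigger threshold. From the documents: 18 participants, DASS-21 at each visit, training visits 2 to 5, stop on a rise between consecutive visits. Everything else below is an assumption.

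**Set-up.** Scores are scaled to SD 1. The measure is mean change from visit 2 to visit 5. A participant is removed if the first rise of at least k × √(2(1−ρ)) occurs at visit 2, 3 or 4. A rise first seen at visit 5 leaves the series complete. ρ is 0.6 or 0.8 and k is 1.645 or 1.96, with 400,000 simulated participants per scenario. In the jump case, 20% of participants have a lasting 1.5 SD rise starting at visit 3, 4 or 5, so the true mean change is 0.20 × 1.5 = 0.30. In the even case, everyone worsens by 0.1 SD per visit, so the true change is 3 × 0.1 = 0.30.

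**Complete-series result** (share hidden = (0.30 − result)/0.30):

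| ρ, k | Jump, constant correlation | Even, constant correlation | Jump, AR(1) | Even, AR(1) |
|---|---|---|---|---|
| 0.6, 1.645 | 0.196 (35%) | 0.285 (5%) | 0.089 (70%) | 0.180 (40%) |
| 0.6, 1.96 | 0.221 (26%) | 0.291 (3%) | 0.160 (47%) | 0.232 (23%) |
| 0.8, 1.645 | 0.149 (50%) | 0.287 (4%) | 0.046 (85%) | 0.166 (45%) |
| 0.8, 1.96 | 0.175 (42%) | 0.294 (2%) | 0.106 (65%) | 0.224 (25%) |

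When nobody changes, the result is about 0 under constant correlation and a false improvement of 0.05 to 0.10 SD under AR(1).

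**Number lost, jump case, constant correlation.** Of those who worsen, 31% to 59% are missing; of the others, 7% to 15%. The smallest loss is 18 × (0.2 × 0.31 + 0.8 × 0.07) = 2.1 and the largest is 18 × (0.2 × 0.59 + 0.8 × 0.15) = 4.3. This counts every threshold crossing as a stop.

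**Against sampling error, jump case.** The jump adds variance 0.2 × 0.8 × 1.5² = 0.36.
- Constant correlation: the SD of the mean change in 18 people is √((2(1−ρ) + 0.36)/18), which is 0.25 for ρ = 0.6 and 0.21 for ρ = 0.8. The bias is 0.08 to 0.15.
- AR(1): √((2(1−ρ³) + 0.36)/18) gives 0.33 and 0.27. The bias is 0.14 to 0.25.

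**Where the direction changes.**
- Lasting jump at visit 2, constant correlation: true change 0, complete series +0.02 to +0.03.
- Transient spike at visit 2, 3 or 4, constant correlation: true −0.10, complete series −0.03 to −0.07, so less improvement than the truth.
- Spike at visit 2 only, AR(1): true −0.30, complete series −0.16 to −0.23.
- Jump at visit 5 only, constant correlation: 0.30, no bias.
- Triggering score carried forward, jump case, constant correlation: 0.35 to 0.42, an overstatement.

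**A second set of assumptions.** This counted only rises between the analysed visits, used a trigger of 1 SD or a reliable-change cut, and allowed gradual or abrupt worsening. Complete-series change was at or below the full-group change throughout. With independent errors, a true 0.50 SD worsening in everyone came out as 0.28 to 0.47; with the strict cut and autocorrelated errors the loss was about 0.01.

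**What the fix recovers, jump case, constant correlation** (same order of ρ and k). A random-intercept model on all observed scores, with visit 1 as an outcome, gives 0.232, 0.252, 0.201 and 0.217. The first row removes (0.232 − 0.196)/(0.30 − 0.196) = 35% of the bias; the others remove 39%, 34% and 34%. If half of those stopped keep answering, the results are 0.268, 0.278, 0.256 and 0.261, which removes 69% to 72%. Under AR(1) the shares are 22% to 26% and 65% to 66%.

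**The case against.** The strongest reply is that nothing in the plan says a stop ends data collection or that the ANOVA discards incomplete series. The trigger is undefined too, and 5.4 describes possible review rather than an automatic stop, so fewer people may be lost than the simulation counts. All of that stands. It makes the bias conditional and its size unknown. It does not supply a provision for DASS-21 after a stop: even if only training is stopped, no section says the surveys continue.

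A second reply is that this is an 18-person pilot with no decision resting on the DASS-21 ANOVA. Discomfort counts, daily log review, weekly Co-Investigator review and per-visit retention also still register the stopped participants. That stands as well and keeps the point small. However, none of these gives a DASS-21 course after the stop, and the pilot is meant to inform a larger study, where the same rule would matter more.

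A reader might infer that the plan has a built-in bias that hides harm, or that a quarter to a half of any worsening would be missed. The documents support neither. The handling of incomplete series is unstated, the 26% to 50% range belongs to one assumed pattern, and other patterns give almost no bias or the opposite direction.

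**Conclusion.** The gap is real and can be read from the text: the stopping trigger is the analysed endpoint, and no section covers DASS-21 after a stop. On two assumptions, that stopping ends collection and that the ANOVA uses complete series, participants stopped before the last training visit are excluded because of their own worsening. This usually understates worsening.

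The size is not derivable. The illustrations with a true 0.30 SD worsening run from 2% to 85% hidden. The direction can reverse with a rise at visit 2, transient spikes or carry-forward. In the jump case the bias is below sampling error at 18 participants. The primary feasibility aim is unaffected. This is a worthwhile, inexpensive improvement to a secondary and safety endpoint; confidence is medium.

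**What to change.** Who stops training remains a clinical decision. The changes are:

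1. **Sections 6.5 and 4.4:** distinguish stopping training from ending data collection.
2. **Section 4.3 and consent:** offer stopped participants who agree the DASS-21 REDCap link on the remaining dates and at one month from the scheduled visit 6. Exempt those whose distress came from the study procedures or the surveys, since 6.5 stops people on that ground and 1.3 accepts that surveys may distress.
3. **Section 6.3:** replace a complete-series ANOVA with a repeated-measures mixed model on every observed score, including the triggering score and visit 1 as an outcome. Omitting visit 1 gives a false worsening of about 0.02 to 0.03 SD when nobody changes (constant correlation). Keep the covariance simple: an unstructured one over five visits needs 5 × 6/2 = 15 parameters from 18 people. State that the model only partly removes the bias.
4. **Reporting:** give the number stopped by arm, visit and 6.5 ground, with their individual DASS-21 scores. At this sample size the listing is the most informative item and needs no new data.

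The cost is protocol and consent wording and a few extra links in a system already in use. The downside is a short optional survey for a distressed person, and some will decline.

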7.1 Koru Mindfulness (KM) Intervention Group

Koru Mindfulness is a 4-week mindfulness meditation training initially designed for the emerging adult population (considered \leq 29 years). The skills are intended to help young adults manage stress, and thus can be advertised as an opportunity to learn skills in navigating college without having to mention mindfulness training anywhere in recruitment materials. The intervention will be delivered online through Zoom by a certified Koru instructor, with the goal of assessing the feasibility of an accessible intervention for college students. Koru is delivered with a mix of PowerPoint slides, group training of mindfulness and meditation skills and discussion, and daily logging of practice with an application or journal. The training is accompanied by the book *The Mindful Twenty-Something* [44].

Participants will be encouraged to practice daily any of the mindfulness and meditation skills that were previously learned. To incentivize compliance with training, monetary incentives will be given to individuals who practice ≥ 3 days/week and those who practice ≥ 5 days/week.

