4.2 Intervention procedures (by visits)

See Figure 1 for overview of study visits.

Visit 1

- Written consent, MINI interview [25], urine drug screen and breathalyzer alcohol test, C-reactive protein (CRP) assay, Reward-AB task

Visits 2-5

- Randomization to either the Koru Mindfulness (KM) intervention or the Navigating College (NC) control group.
- Each training visit will consist of the following:
 - Surveys completed online through REDCap.
 - 75 minutes of instructor-led discussion
 - Breakout sessions for participants to share their thoughts and experiences in response to instructor's prompt.

Navigating College (NC) Control Group Training

Topics discussed during each training visit include: habits, roommate issues, homesickness, the internet (week 1); strategies when sinking, study skills, getting involved, habit formation (week 2); HALT, gateway habit (week 3); and academic success tips, taking notes, and procrastination (week 4).

Koru Mindfulness (KM) Intervention Training

Topics discussed during each training visit include: belly breathing, dynamic breathing, body scan (week 1); walking meditation, gatha (week 2); guided imagery, labeling thoughts (week 3); eating meditation, and labeling feelings (week 4).

Daily Logging of Skills

Participants in the CG intervention will be asked to journal by hand or via Qualtrics every day for ≥ 10 minutes, on anything related to the topics learned during that week's training visit. Participants in the KM intervention will

be asked to practice every day for ≥ 10 minutes any mindfulness or meditation skill previously learned during training visits, in addition to logging their practice and reflection using the Koru application.

Visit 6

- Similar to visit 1, without repeating the MINI interview.

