7.1 Navigating College (NC) Control Group

The NC training is designed to match the KM training in at least the total duration of the training, the duration of each individual visit, the practice of daily training of a skill, class structure, and instructor. The skills taught are directly related to the topics discussed in the *Freshman Survival Guide: Soulful Advice for Studying, Socializing, and Everything In Between* [19].

Participants will be encouraged to write in their paper journal or online (via Qualtrics) for about 10 minutes every day. Prompts with suggested topics for reflection will be provided.

STUDY INTERVENTION ADMINISTRATION

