8.1 Administration for Training Groups

After Visit 1, participants will be randomized to either the intervention or control group using a randomized number computer generator (e.g., 01-18 assigned to mindfulness meditation group). The NC and KM training instructor will be blinded to the group each participant is randomly assigned to, and participants will be assigned a unique ID to put as their name for their Zoom profile and on questionnaires. This number will be given (and recorded) by a research assistant. During training visits, all videos (except the instructor's) will be turned off.

SAFETY MANAGEMENT

We do not anticipate participant safety to be an issue in this study. Proposed procedures do pose a risk of harm if safety protocols are not followed carefully. To ensure participant safety, all participants will be thoroughly screened by trained personnel for the presence of conditions that could pose a threat to the subject. All research personnel will be trained in blood collection by finger prick. Daily practice logs will give participants a safe space to share any discomfort experienced during training. If participants in the KM group are experiencing extreme discomfort during weeks when visits 2-6 take place, due to resurfacing of traumatic experiences, subjects will be withdrawn from the study and given resources to alleviate distress. Logs will be checked daily. Any adverse event related to the training or blood collection will be immediately reported to the Principal and Co-Investigators.

DATA COLLECTION AND MANAGEMENT

We will obtain a certificate of confidentiality for this study. A participant's personal information could be linked with their study data. To minimize this risk, no one outside of the research team will have access to participants' data. Participants' data will only be identified in all computer analyses with their ID numbers. Any paperwork that includes participants' names or other personal information will be stored in a locked file cabinet in the locked lab. All data will be archived without personal identifiers, using only ID numbers. Emails to participants will be encrypted.

RECRUITMENT STRATEGY

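### The safety measure is a raw count of discomfort reports with no denominator or by-arm summary, while the chance to report through the daily logs may differ between arms

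*Combined protocol and SAP*

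**What the plan says.** **Safety measure.** Section 6.3: "The number of times discomfort is reported by participants with any training procedure will be used as a measure of safety". It does not say what counts as one report, over what period reports are counted, what they are divided by, or whether the arms are shown separately. No between-arm test of discomfort is planned.

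**Channels.** The Safety Management text after section 8.1 says: "Daily practice logs will give participants a safe space to share any discomfort experienced during training". Section 6.5 also uses the written entries of both arms as a trigger for stopping a participant. Logs are not the only route. The synopsis says "the teacher will regularly check in with students to address any concerns", section 1.3 has participants observed for discomfort, and section 5.4 gives the DASS-21 at every visit.

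**Log volume.** In the KM arm, "monetary incentives will be given to individuals who practice ≥ 3 days/week and those who practice ≥ 5 days/week". KM practice is recorded by participants themselves, "in addition to logging their practice and reflection using the Koru application" (section 4.2). For the NC arm the text is "Participants will be encouraged to write in their paper journal or online (via Qualtrics) for about 10 minutes every day". The NC section does not mention payment. Its list of features matched to KM ends with "the practice of daily training of a skill, class structure, and instructor" and is worded as a minimum.

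**Log review.** Section 5.4 names the KM instructor as the daily reader. The Safety Management text says logs are checked daily but names no reader. NC participants may write on paper, and how paper entries reach a reader each day is not described.

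**Stopping.** Under section 6.5, a participant who attributes discomfort of any degree to the study procedures is stopped. Section 4.4 and the Safety Management text describe withdrawal of KM participants for extreme discomfort.

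**The concern.** A participant who writes more entries has more occasions to mention discomfort, and an entry that is read daily is more likely to be counted. If either differs between KM and NC, the count in section 6.3 differs even when the underlying discomfort is the same. Section 2.1 says the pilot is to inform a larger study. A high count in KM could be read as the training being poorly tolerated when participants simply logged more, and a low count could hide discomfort that was not written down.

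The payment question also reaches the primary endpoint. Section 6.1 measures compliance by mean entries per week in each group, and section 6.3 uses "The mean number of self-report training or journaling days recorded by participants". If only one arm is paid for its daily task, a difference in these figures cannot be separated from the payment.

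**Working it through.** The plan states no expected discomfort count, report rate or logging frequency, so it has no figure of its own to reproduce. The allocation is consistent: 9 + 9 = 18.

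**Inputs from the documents.** 9 participants per arm (sections 3.2 and 3.3); 4 weeks of training (synopsis); KM payment thresholds of 3 and 5 practice days/week (section 7.1, KM).

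**Assumed inputs.** The chance p of a discomfort report per log entry is the same in both arms: 5%, with 1% to 10% as the range. Entries are independent, and logs are treated as the only channel. KM logs 5 or 3 days/week, NC 2 or 5.

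**Step 1. Entries per participant.** 5 × 4 = 20; 3 × 4 = 12; 2 × 4 = 8.

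**Step 2. First report only.** Read literally, section 6.5 stops a participant after one procedure-related report, so each contributes at most one. Expected participants with a report = 9 × [1 − (1 − p)^entries]. At p = 0.05:

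- 20 entries: 9 × (1 − 0.95^20) = 5.77
- 12 entries: 9 × (1 − 0.95^12) = 4.14
- 8 entries: 9 × (1 − 0.95^8) = 3.03

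| p per entry | 5 v 2 days/week | 3 v 2 days/week | 5 v 5 days/week |
|---|---|---|---|
| 1% | 1.6 v 0.7 | 1.0 v 0.7 | 1.6 v 1.6 |
| 2% | 3.0 v 1.3 | 1.9 v 1.3 | 3.0 v 3.0 |
| 5% | 5.8 v 3.0 | 4.1 v 3.0 | 5.8 v 5.8 |
| 10% | 7.9 v 5.1 | 6.5 v 5.1 | 7.9 v 7.9 |

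**Step 3. Repeat reports allowed.** Expected count = 9 × entries × p. At p = 0.05 and 5 v 2 days: 9 × 20 × 0.05 = 9.0 against 9 × 8 × 0.05 = 3.6. The ratio, 2.5, is just 5/2, the assumed logging ratio. Whether step 2 or step 3 applies depends on which stopping text governs.

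**Step 4. Reports withheld.** If KM participants withhold a share s of their reports, the ratio in step 3 is multiplied by (1 − s). At 5 v 3 days it is (5/3)(1 − s): 1.67 at s = 0, 1.33 at 20%, 1.00 at 40% and 0.67 at 60%. The direction can reverse.

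**Step 5. With a denominator.** At 5 v 2 days, 9.0 reports in 9 × 20 = 180 entries and 3.6 in 9 × 8 = 72 entries both give 5 per 100 entries. The volume effect disappears. Withholding is not corrected: at s = 40% KM would show 5 × 0.6 = 3 per 100.

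**The case against.** A reader might go further and infer that NC participants are unpaid, that KM participants are paid to write logs, that the count is therefore inflated in KM, and that they have a financial reason to stay silent. The documents do not support these as facts.

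- **One-arm payment** rests on silence. The matching list is open-ended, and KM participants are also only encouraged to practise daily, so that word does not separate the arms.
- **Payment is for practice days.** Logs are how those days become known; that payment raises log volume is a plausible inference.
- **A motive to withhold** is inferred from section 6.5. No section says what happens to incentives when someone is stopped, and the rule covers both arms' entries.
- **Direction.** More logging and withheld reports act in opposite ways, so no direction can be claimed.
- **The 9.0 v 3.6 contrast** needs repeat reports, which section 6.5 read literally would largely prevent.
- **More practice is more exposure.** Some excess in KM could be real burden. A fixed chance per entry makes all of it artefact by construction.
- **The reader of the logs** may be the same person in both arms, since instructor is a matched feature. The text does not say.

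It is also fair that safety is not the primary endpoint, that no arm comparison of discomfort is tested, and that the DASS-21 and teacher check-ins give other safety information. All of this limits the claim. None of it gives the count in section 6.3 a denominator, a by-arm summary or an equal opportunity to report.

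**Conclusion.** The point holds as a weakness of measurement, not as a demonstrated bias. The count in section 6.3 cannot be interpreted without knowing how many chances to report each arm had, and the plan leaves open whether those chances are equal. On the first-report basis the possible distortion ranges from none with equal logging to about one participant (4.1 v 3.0) at 3 v 2 log days/week and about three (5.8 v 3.0) at 5 v 2, out of 9 per arm. These figures rest on an assumed 5% chance per entry, equal in both arms, and on assumed logging rates; the documents give neither. The net direction is unknown. The harm is to interpretation, since no test depends on the count. The incentive bears more directly on entries per week in section 6.1, where its status in NC must be known before the arms are compared.

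**What to change.** 1. **Section 6.3.** Add one fixed discomfort item (yes/no and intensity) to the REDCap survey already given at each training visit, and to visit 6, in both arms. Make the safety measure the number of participants with at least one 'yes', by arm, shown with the number of visits at which the item was answered, because missed visits and stopping reduce that number. Surveys open each visit, so the visit 2 answer precedes the first class and is best shown separately as a baseline. That leaves visits 3 to 6, four occasions for everyone who attends.
2. **Supportive summary.** Report spontaneous log reports per entry submitted, by arm. Section 6.1 already requires the entry counts. State who reads the NC entries, including those on paper, and how often.
3. **Incentive.** State whether NC journaling carries the same incentive. If it does not, either equalise the schedule or describe the by-arm entries per week in section 6.1 as confounded by payment.
4. **Stopping text.** Reconcile section 6.5 with section 4.4 and the Safety Management text. Which one governs determines how many reports one participant can contribute.

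The cost is one survey item, a few sentences and, if the schedule is equalised, a small payment budget for 9 control participants. The downside is that asking directly will raise the number of reports somewhat in both arms. A fixed item does not remove every reason to withhold, but it puts the same question to everyone.
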